### 4.1.2 Secondary efficacy Endpoints

The Secondary efficacy endpoints of this study are:

Healthy Controls in Both Arms 1 and 2:

- Applicability of the Normal (Gaussian) distribution to TUVjoint data.
- Relationship between TUVjoint and age by joint.
- Relationship between the variance of TUVjoint and age.
- Relationship between TUVjoint and sex (male vs female).
- Relationship between TUVjoint and BMI.

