#### 4.2 Analysis of Efficacy Variables

#### 4.2.1 Analysis of Primary Efficacy Variables

#### Arm 1:

All TUVjoint data will be analyzed with summary statistics (mean, standard deviation, n, minimum, median, maximum) by reader, joint and view.

The 5 and 95 percentiles will be estimated with quantile regression fitting an intercept as a fixed term. The lower and upper limits of normal TUVjoint will be determined using non-parametric confidence intervals and kernel density-based confidence intervals.

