### 4.2.2 Analysis of Secondary Efficacy Variables

Healthy Controls in Both Arms 1 and 2:

Normal quantile plots will be provided per-joint and reader, along with the p-value for the Shapiro-Wilk test of Normality.

Scatter plots of  $TUV_{joint}$  by age per-joint will be provided, along with the correlation coefficients and p-values. The hypotheses for the p-value to test the correlation coefficient are:  $H_0$ :  $\rho = 0$  vs  $H_1$ :  $\rho \neq 0$ , where  $\rho$  is the correlation coefficient. The p-value evaluating age in the regression model will be provided in the figure.

Scatter plots of  $TUV_{joint}$  by BMI will be provided, along with the correlation coefficients and p-values. The hypotheses for the p-value to test the correlation coefficient are:  $H_0$ :  $\rho = 0$  vs  $H_1$ :  $\rho \neq 0$ , where  $\rho$  is the correlation coefficient. The p-value evaluating BMI in the regression model will be provided in the figure.

Scatter plots of TUVjoint by sex will be provided.

To check the relationship between the variance of TUVjoint and age, a quantile regression model will be fitted with an intercept as a fixed term. The plot of the residuals on the y-axis and age on the x-axis will be provided.

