# 7.0 List of Analysis Tables, Figures and Listings

Table No.	Table Title	Included in Final Tables	Shown in Appendix B
1	Subject Disposition by Study Arm	X	X
2	Demographics and Baseline Data Summary Statistics by Arm – Continuous Variables (Safety Population)	Х	Х
3	Demographics and Baseline Data Summary Statistics by Arm – Categorical Variables (Safety Population)	Х	Х
4	Summary of Study Drug Administration by Arm (Safety Population)	Х	Х
5	Summary of TUV joint on both Arms Per Reader, Joint, and View (ITD population)	Х	Х
6	Summary of TUV joint on both Arms Per Reader, Joint, and View (PP Population)	Х	
7	Summary of SUV on Arm 2 per Joint and a Total of All Joints (ITD population)	Х	Х
8	Summary of SUV on Arm 2 per Joint and a Total of All Joints (PP Population)	Х	
9	Normal Range of TUV joint for the Three Blinded Readers in All Arm 1 and 2 Healthy Control Subjects (ITD Population)	Х	Х
10	Normal Range of TUV joint for the Three Blinded Readers in All Arm 1 and 2 Healthy Control Subjects (PP Population)	Х	
11	Correlation Between TUV joint and Age and BMI – All Arm 1 and 2 Healthy Control Subjects (ITD Population)	Х	Х
12	Correlation Between TUV joint and Age and BMI – All Arm 1 and 2 Healthy Control Subjects (PP Population)	Х	
13	Frequency Counts and Percentage of Localization in SPECT/ CT Imaging in RA Subjects (ITD Population)	Х	Х
14	Frequency Counts and Percentage of Localization in SPECT/ CT Imaging in RA Subjects (PP Population)	Х	
15	Shapiro-Wilk P-Value for Normality Test for TUV joint Data – All Arm 1 and 2 Healthy Control Subjects (ITD Population)	Х	Х
16	Shapiro-Wilk P-Value for Normality Test for TUV joint Data – All Arm 1 and 2 Healthy Control Subjects (PP Population)	Х	
17	Predictive Value of Planar Scans for SPECT/CT Per Joint and Reader (ITD Population)	Х	Х
18	Predictive Value of Planar Scans for SPECT/CT Per Joint and Reader (PP Population)	Х	
19	Number and Percentage of Subjects with TEAEs (Safety Population)	Х	Х
20	Summary of TEAEs (Safety Population)	Х	Х
21	Number and Percentage of Subjects with TESAEs (Safety Population)	Х	Х
22	Number and Percentage of Subjects With TEAEs by Severity Grade (Safety Population)	Х	Х
23	Number and Percentage of Subjects With TEAEs by Level of Relationship to Tc 99m Tilmanocept (Safety Population)	Х	Х
24	Number and Percentage of Subjects With TEAEs by Level of Relationship to Procedure (Safety Population)	Х	

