	Healthy Control Subjects (ITD Population)		
Fig32	Scatter Plot of TUV joint Distribution by BMI – All Arm 1 and 2	Х	
	Healthy Control Subjects (PP Population)		
Fig33	Scatter Plot of Residuals by Age – All Arm 1 and 2 Healthy	X	X
	Control Subjects (ITD Population)		
Fig34	Scatter Plot of Residuals by Age – All Arm 1 and 2 Healthy	X	
	Control Subjects (PP Population)		

Listing No.	Data Listing Title	Included in Final Listings	Shown in Appendix B
DL1	Subject Disposition Data Listing	X	X
DL2	Inclusion/Exclusion Data Listing	Х	Х
DL3	Protocol Deviations Data Listing	Х	Х
DL4	Demographics Data Listing	Х	Х

Listing No.	Data Listing Title	Included in Final Listings	Shown in Appendix B
DL5	Subjects Excluded from ITD Population Data Listing	X	X
DL6	Subjects Excluded from PP Population Data Listing	X	X
DL7	Subjects Excluded from Safety Population Data Listing	X	X
DL8	Medical History Data Listing	X	Х
DL9	Prior and Concomitant Medications Data Listing	X	Х
DL10	Prior and Concomitant RA Medications Data Listing	Х	Х
DL11	Adverse Events Data Listing	Х	Х
DL12	Subject Laboratory Profiles – Hematology Data Listing	Х	Х
DL13	Subject Laboratory Profiles – Serum Chemistry Data Listing	Х	
DL14	Subject Laboratory Profiles – Urinalysis Data Listing	Х	
DL15	Subject Laboratory Profiles – Rheumatology Panel Data Listing	Х	
DL16	Physical Exam Data Listing	Х	Х
DL17	ACR/EULAR 2010 Classification Data Listing	Х	Х
DL18	DAS-28 by Joint Data Listing – Arm 2 RA Subjects	Х	Х
DL19	DAS-28 by Subject Data Listing – Arm 2 RA Subjects	Х	Х
DL20	Vital Signs Data Listing	Х	Х
DL21	Study Drug Administration Data Listing	Х	Х
DL22	Post-Injection Imaging Data Listing	Х	Х
DL23	SPECT/CT Reader Results Data Listing – Hands and Wrists	Х	Х
DL24	TUV Data Listing	Х	Х

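### The SAP's check of TUVjoint variance against age names only an intercept, so its residual plot keeps any age trend in level and no listed output estimates how spread changes with age

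*SAP*

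**What the plan says.** SAP 4.1.2 lists "Relationship between the variance of TUV joint and age" as a secondary endpoint for healthy controls in both arms. It is separate from the endpoint on the relationship between TUVjoint itself and age.

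SAP 4.2.2 answers it as follows: "a quantile regression model will be fitted with an intercept as a fixed term. The plot of the residuals on the y-axis and age", with age as the horizontal axis. No age term, quantile level, estimate, interval or reading rule is given. SAP 4.2.1 uses the same phrase for the primary limits: "The 5 and 95 percentiles will be estimated with quantile regression fitting an intercept as a fixed term". There it plainly means one marginal quantile.

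The only output for the endpoint is Figures 33 and 34 in SAP 7.0, titled "Scatter Plot of Residuals by Age", one for each analysis population. Their titles name no joint, whereas Figures 7 to 28 (TUVjoint by age) are titled joint by joint.

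The trend in level is handled elsewhere in 4.2.2, by a correlation coefficient and its p-value, and "The p-value evaluating age in the regression model will be provided in the figure".

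**The concern.** A question about variance needs level and spread to be separated. A residual plot does this only if the model behind it has removed the dependence of level on age. A model without age removes nothing that depends on age, so the reader sees trend and fanning together. The plan also supplies no estimate to settle what the eye makes of it.

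At stake is one descriptive endpoint. It has some substance, because the study is building a normative database with enrolment stratified by age, and one 95th percentile per reader and joint, with no age term, then classes planar joints as positive. Whether spread changes with age bears on how well a single limit suits all ages.

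**Working it through.** The plan states no figure for this endpoint, so there is none to reproduce. The check is algebra, a numerical confirmation, and a search of the listed outputs.

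**Inputs from the documents.** Model terms: SAP 4.2.2 and 4.2.1. Healthy controls: 120 + 5 = 125 (SAP 1.3). DAS28 joints in the hands and wrists: 22. Views: 2. Blinded readers: 3. Joint types in Figures 7 to 28: 11 (MCP1–5, PIP1–5, wrist). The documents give no TUV SD and no age slope.

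**Step 1: algebra.** An intercept-only quantile regression at level τ returns one constant c, the sample τ-quantile. Hence, within one fit:

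- residual = TUV − c
- mean(residual | age) = mean(TUV | age) − c, so the whole trend in level remains
- var(residual | age) = var(TUV | age)
- corr(residual, age) = corr(TUV, age)

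Changing τ changes c, which moves the zero line and nothing else.

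**Step 2: numerical confirmation.** One invented data set with n = 125 was fitted at three quantiles.

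| τ | fitted intercept | SD of (TUV − residual) | corr(residual, age) | corr(TUV, age) |
|---|---|---|---|---|
| 0.05 | 0.839 | 0 to rounding | 0.4646 | 0.4646 |
| 0.50 | 0.969 | 0 to rounding | 0.4646 | 0.4646 |
| 0.95 | 1.230 | 0 to rounding | 0.4646 | 0.4646 |

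The value 0.4646 belongs to the invented data. The equality is the result.

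**Step 3: pooled joints.** If one intercept serves several joints, the variance of the plotted points at a given age is the average within-joint variance plus the variance of the joint means. The second part is not the spread the endpoint is about.

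**Step 4: other listed outputs.**

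- Tables 11 and 12, "and Age and BMI – All Arm 1 and 2 Healthy Control Subjects (ITD Population" and the PP counterpart, give correlations of TUV with age and BMI. These concern level.
- Tables 5, 6, 9 and 10 give SDs by reader, joint and view, never by age.
- Figures 7 to 28 show TUVjoint by age per joint, with no measure of spread.

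None of these estimates change in spread with age.

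**Step 5: size of the remedy.** Series: 22 × 2 × 3 = 132, or 11 × 2 × 3 = 66 with sides combined. If spread did not change with age, 132 × 0.05 = 6.6, so about 7 of the 95% intervals would exclude 0 by chance.

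Precision can be illustrated only under assumptions. Take Normal errors, the planned age mix, n = 125, and SD = exp(0.1 × decades from age 55). The mean of |residual| is about 0.798 SD, so the expected slope is about 0.798 × 0.1 = 0.080 SD per decade. The simulated bootstrap SE was 0.0381, giving a half-width of 1.96 × 0.0381 = 0.075. At that assumed rise the interval is nearly as wide on each side as the slope itself.

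**The case against.** **An age term may be intended.** The SAP says the model has an intercept as a fixed term; it does not say that it has nothing else. This cannot be excluded. But no age term is named, and the identical phrase in 4.2.1 describes an intercept-only fit. If age was meant, the residuals would be free of the linear trend and only the missing estimate would remain. The SAP needs the wording corrected either way.

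**A plot is a legitimate check.** The SAP's verb is to check, a residual plot is an ordinary way to look for fanning, and the sex endpoint is also answered by scatter plots alone. This stands in part. Since the residuals are TUV shifted by a constant, no information on spread has been lost and a reader can see marked fanning. A reader might infer that the plot is uninformative; the documents do not support that. What remains is that level and spread are mixed and nothing is quantified, when both can be remedied cheaply.

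**Figures 33 and 34 may not duplicate earlier figures.** A reader might infer that they simply repeat Figures 7 to 28. That follows only for intercept-only fits within a single series. Figures 33 and 34 are not titled per joint. Pooled under one intercept, they would copy no per-joint figure; with joints centred separately and overlaid, they would remove level differences between joints that Figures 7 to 28 do not. The Appendix B graphic is not visible in the text available here, so its layout cannot be judged.

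**Conclusion.** The point holds, with low consequence. On the plain reading of SAP 4.2.2, the planned plot does not separate a change in spread from a change in level, and no listed output estimates the first. The identity in Step 1 is exact but conditional on an intercept-only model, fitted within one joint, view and reader.

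Three further inferences are not supported:

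- **That the primary limits are affected.** The 5th and 95th percentile estimates come from a separate fit and do not change.
- **That the unstated quantile distorts the plot.** In a plot of signed residuals it moves only the zero line.
- **That a given method would detect a change in spread with some known higher probability.** The documents give no TUV SD or age slope, so any such rate describes assumed effects, not this trial. The precision figure in Step 5 has the same limit and is there only to show that intervals may be wide.

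**What to change.** In SAP 4.2.2:

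- Replace the model with a median (50th percentile) regression containing an intercept and age, fitted at least per joint and reader, and per view if the limits are view-specific.
- Plot the residuals from that fit against age in Figures 33 and 34, repeated per joint.
- Report one descriptive measure: the slope of |residual| on age, with a 95% CI from a bootstrap that resamples subjects and refits the median line each time. If sides are combined, keep both sides of a subject together.
- Take |residual| from the age-adjusted median fit, not from an intercept-only fit. For example, with an intercept at the 5th percentile nearly all residuals are positive, so |residual| is nearly the residual itself and its slope on age would mostly reflect the trend in level.

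The cost is SAP wording and programming on data already collected. The protocol does not list this endpoint, so it needs no amendment. The downsides are more output (up to 132 series, or 66 with sides combined), no multiplicity control and modest precision. The SAP should say that the intervals are descriptive. A straight age line also leaves any curvature in level in the residuals; the revised figures would let a reader look for it.

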#### Arm 2:

SUV will be calculated and summarized on both a per-joint and a total of all joints with summary statistics: mean, standard deviation, n, minimum, maximum, and median. The formula for SUV is:

$$SUV = \frac{r}{(a'/w)};$$

where:

r: The radioactivity activity concentration [kBq/mL]

a': The decay-corrected amount of injected radiolabeled FDG [kBq]

w: The weight of the patient [g]

The predictive value of planar scans for SPECT/CT qualitative findings will be summarized per joint and reader with a crosstabulation and the uncertainty coefficients for row | column, column | row, and symmetric. The planar result will be deemed "positive" (i.e., inflamed) if TUVjoint > 95 percentile of the reader.

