9.5.3 Analysis of Efficacy Variables

All efficacy analyses will be conducted on both the ITD and PP populations. The ITD population will be the primary analysis set.

9.5.3.1 Primary Endpoint Arm 1

The distribution of TUV_{joint} in HC subjects will be summarized with descriptive statistics: mean, standard deviation, n, minimum, maximum, and median per reader, joint, and view. The 5 and 95 percentiles will be estimated with quantile regression fitting an intercept as a fixed term. The lower and upper limits of normal TUV_{joint} will be determined using non-parametric confidence intervals and kernel density-based confidence intervals.

9.5.3.2 Primary Endpoint Arm 2

Localization of tilmanocept in the hands and wrists will be summarized with frequency counts and percentages by reader and joint.

9.5.3.3 Secondary Endpoint Arm 1

Normal quantile plots will be provided per joint and reader, along with the *p*-value for the Shapiro-Wilk test of Normality.

9.5.3.4 Secondary Endpoints Arm 2

SUV will be calculated and summarized on both a per-joint and a total of all joints with summary statistics: mean, standard deviation, n, minimum, maximum, and median.

The predictive value of planar scans for SPECT/CT qualitative findings will be summarized per joint and reader with a crosstabulation and the uncertainty coefficients for row | column, column | row, and symmetric. The planar result will be deemed "positive" (i.e., inflamed) if $TUV_{joint} > 95$ percentile of the reader results for the same joint in Arm 1. Otherwise, the planar result will be deemed "negative".

Additional efficacy analyses may be described in the NAV3-35 Statistical Analysis Plan (SAP).

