### 1.2 Study Procedures

Subjects will visit the study site (Visit 1) for screening procedures up to 30 days (Day -30 to Day -1) before enrollment into the study. Screening procedures (demographics, vital signs, medical history, blood and urine samples for clinical labs, RA specific labs, urine pregnancy testing for subjects of childbearing potential, and physical exam) will be completed along with the 2010 ACR/EULAR score. RA subjects will also undergo a DAS28 evaluation and a review of RA history including previous treatments, date of symptom onset, and date of diagnosis.

Subjects arriving for Study Day 0 (Visit 2) will be considered enrolled in the study. On Day 0 subjects will receive Tc 99m injection and imaging procedures. A urine pregnancy test will be administered (pre-injection) to all subjects with childbearing potential. Up to 30 minutes prior to drug administration assessment of vital signs and AEs will be performed. After pre-injection procedures are completed subjects will receive a single IV dose with 150  $\mu g$  of tilmanocept radiolabeled with 10 mCi of Tc 99m. Within 30 minutes of injection, subjects will receive vital sign and AE check. For all subjects, planar images of the bilateral hands and wrists will be taken at 60 - 75 minutes for 10 – 13 minutes. After preparation up to 10 minutes, for Arm 2, SPECT/CT of the bilateral hands and wrists will be acquired for 25-30 minutes.

On Study Day 5 ( $\pm$  3 days) (Visit 3) a safety follow-up telephone call will include a review of concomitant medications and assessment of adverse events. Subjects have completed the study at this point.

For all subjects, delegated trained imaging scientists blinded to all clinical subject information will perform semi-automated region-of-interest ROI drawing on planar images of the bilateral hands and wrists to derive relevant count statistics, which are input parameters for TUVjoint and TUVglobal.

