#### 1.3 Sample Size

The study will enroll up to 135 evaluable subjects in Arms 1 and 2 allocated below, imaged at up to 8 study centers.

Arm 1 will have up to N = 120 evaluable HC subjects, Arm 2 will have up to N = 15 evaluable subjects; 5 HCs and 10 RA subjects.

A subject is considered evaluable if he/she meets the criteria for the analysis population and has the data necessary for computing the primary endpoint(s) relevant to his/her study Arm.

The sample will be stratified 3:1, females to males ratio to reflect RA incidence in the United States. The sex-specific samples will be further stratified by age to reflect the Census estimated US population in 2019.

The target sample sizes are given below.

Age Range	Male	Female	Total
30 to 39 years	8	23	31
40 to 49 years	7	21	28
50 to 59 years	8	22	30
60 to 69 years	7	21	28
70 years and older	6	21	27
Total	36	108	144

An effort will be made to target enrollment in this group to include 2 men and 8 women 80 years old and over.

The existing data for HC subjects was used in a bootstrap procedure to evaluate the width of 95% confidence intervals for the 95 percentiles for various sample sizes. The sponsor has decided for its business purposes that knowing the percentile to within 0.05 of its true value is sufficient. A sample of size N = 144 HC results (this includes the subjects from Arm 1 of NAV3-31) in 95% confidence intervals with half-widths less than 0.05.

The sample size for Arm 2 was determined to be sufficient for the business purposes of the sponsor. The sample size for Arm 2 will be 5 HCs and 10 RA subjects.

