#### Localized on SPECT/CT

Joint	Reader	No	Yes	Total
xxxxxxxxxxx	xx	xxx	xxx	XXX
		XX.X%	xx.x%	
	xx	xxx	xxx	XXX
		XX.X%	xx.x%	
	xx	xxx	xxx	XXX
		xx.x%	XX.X%	

STATKING Clinical Services (DD-MMM-YYYY) Source Program: xxxxxxx.sas

Table format is repeated for the PP population.

Page x of y

Table 15. Shapiro-Wilk P-Value for Normality Test for TUVjoint Data - All Arm 1 and 2 Healthy Control Subjects

Navidea Biopharmaceuticals - Study No. NAV3-35

ITD Population (N=xxx)

Test for Normality

Test	Statistic	P-Value
Shapiro-Wilk	xxx	xxx

STATKING Clinical Services (DD-MMM-YYYY) Source Program: xxxxxxx.sas

All Table format is repeated for the PP population

Page x of y

Table 17. Predictive Value of Planar Scans for SPECT/CT Per Joint and Reader
Navidea Biopharmaceuticals - Study No. NAV3-35

ITD Population (N=xxx)

SPECT/CT (Standard of Truth)

Reader	Joint	Planar Scans	Positive	Negative	Total	Uncertainty Coefficients	Estimated 95 %tile
XX	XXX	TUVjoint > 95 (Positive)	XXX	XXX	XXX	XXX	XXX
		Negative	XXX	XXX	XXX		
		Total	XXX	xxx	XXX		
	XXX	TUVjoint > 95 (Positive)	XXX	xxx	xxx	xxx	XXX
		Negative	XXX	XXX	xxx		
		Total	XXX	XXX	XXX		
xx	xxx	TUVjoint > 95 (Positive)	xxx	XXX	xxx	xxx	xxx
		Negative	XXX	XXX	XXX		
		Total	XXX	XXX	XXX		
	xxx	TUVjoint > 95 (Positive)	xxx	XXX	XXX	XXX	XXX
		Negative	XXX	XXX	XXX		
		Total	XXX	xxx	XXX		
XX	XXX	TUVjoint > 95 (Positive)	XXX	xxx	xxx	xxx	xxx
		Negative	XXX	XXX	XXX	*****	*****
		Total	XXX	XXX	XXX		
	xxx	TUVjoint > 95 (Positive)	xxx	xxx	xxx	xxx	xxx
		Negative	XXX	XXX	XXX		
		Total	XXX	XXX	XXX		

If there are no major protocol deviations, then analysis tables for the ITD and PP populations will contain identical results. STATKING Clinical Services (DD-MMM-YYYY)
Source Program: xxxxxxx.sas

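### As laid out, Tables 17 and 18 do not separate the 5 healthy controls from the 10 RA subjects, so the planar versus SPECT/CT association can partly reflect disease status alone

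*SAP*

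**What the plan says.** The predictive value of planar for SPECT/CT is a secondary endpoint of Arm 2. SAP 4.2.2 specifies "The predictive value of planar scans for SPECT/CT qualitative findings will be summarized per joint and reader with a crosstabulation", reported with "uncertainty coefficients for row | column, column | row, and symmetric". Protocol 9.5.3.4 specifies the same analysis. On composition, SAP 1.3 states "Arm 2 will have up to N = 15 evaluable subjects; 5 HCs and 10 RA subjects".

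A planar joint is positive when TUV_joint exceeds the 95th "percentile of the reader results for the same joint in Arm 1" (Protocol 9.5.3.4). SAP 4.2.2 gives the same cut-off without naming the reference group.

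SAP 7.0 titles Table 17 "Predictive Value of Planar Scans for SPECT/CT Per Joint and Reader (ITD Population"), with no restriction to RA subjects; Table 18 repeats it for the PP population. The Appendix B shell has columns for reader, joint, planar result, SPECT/CT result, the coefficients and the percentile, but none for HC or RA. It heads the SPECT/CT columns "SPECT/CT (Standard of Truth").

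Two other Arm 2 outputs do handle disease group. Table 7 (SUV) has separate HC-2 and RA blocks, and Table 13 (SPECT/CT localization) is titled for RA subjects only.

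The documents disagree on who is scanned. SAP 1.2 says "for Arm 2, SPECT/CT of the bilateral hands and wrists will be acquired for 25-30 minutes", and Protocol Table 4, Protocol Appendix 1, SAP Table 1 and the HC-2 rows of Table 7 agree that SPECT/CT covers the whole arm. A footnote to Data Listing 22 limits SPECT/CT to the RA subjects of Arm 2.

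**The concern.** The cut-off comes from healthy controls, so about 1 HC joint in 20 is planar-positive per view by design. The RA subjects are selected for active disease, so one would expect them to be positive more often on planar, and on SPECT/CT too. When two groups differ on both margins, putting them in one 2x2 table creates association between the scans even if, among RA subjects, a positive planar joint says nothing about SPECT/CT for that joint.

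A reader of Table 17 could then take a contrast between healthy and diseased people for joint-level prediction. Row proportions read off the table would also depend on the 5:10 mix, which SAP 1.3 bases on the sponsor's business purposes rather than on any clinic population.

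Separately, calling SPECT/CT the standard of truth assumes what Arm 2 is meant to find out: detection of localization by SPECT/CT is its own primary question.

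**Working it through.** **Plan's own figures.** 5 + 10 = 15 in Arm 2, and 120 + 15 = 135 overall. Both reproduce. No precision, expected rate or target is given for this endpoint, so the positivity rates below are assumptions.

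**Inputs.** RA weight w = 10/15 = 2/3 (SAP 1.3). HC positivity h = 5% on both scans: for planar this follows from the cut-off, for SPECT/CT it is assumed. RA positivity r is the same on both scans and is varied. Planar and SPECT/CT are independent within each group, so the true within-group uncertainty coefficient U is 0 and the odds ratio is 1.

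**Formulas.**
- Margin: m = w·r + (1 − w)·h
- Both positive: p11 = w·r² + (1 − w)·h²
- Discordant cells: p12 = p21 = m − p11
- Both negative: p22 = 1 − 2m + p11
- Mutual information: I = H(row) + H(column) − H(joint), where H is entropy
- Symmetric U = 2I / [H(row) + H(column)]. The margins are equal here, so all three planned coefficients coincide.

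**Worked case, r = 70%.** m = (2/3)(0.70) + (1/3)(0.05) = 0.4833. p11 = (2/3)(0.49) + (1/3)(0.0025) = 0.3275. p12 = 0.1558 and p22 = 0.3608. Then H(row) = H(column) = 0.6926, I = 0.0724, and U = 0.0724/0.6926 = 0.105.

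**Combined table, no association within either group:**

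| RA positivity | Symmetric U | Odds ratio | SPECT/CT-positive among planar-positive | SPECT/CT-positive overall |
|---|---|---|---|---|
| 30% | 0.006 | 1.6 | 28% | 22% |
| 50% | 0.03 | 2.4 | 48% | 35% |
| 60% | 0.06 | 3.2 | 58% | 42% |
| 70% | 0.105 | 4.9 | 68% | 48% |
| 80% | 0.19 | 9.3 | 78% | 55% |
| 90% | 0.37 | 28.9 | 88% | 62% |

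With HC positivity near 10% on both scans, U at 30%, 50%, 70% and 90% is about 0.002, 0.02, 0.08 and 0.30. If RA positivity equals HC positivity at 5%, U = 0.

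**Small-sample behaviour.** Mean symmetric U from simulation (20,000 tables per case, same null, averaged over tables with no empty margin):

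| RA positivity | Combined, n = 15 | RA only, n = 10 |
|---|---|---|
| 30% | 0.096 | 0.119 |
| 50% | 0.096 | 0.104 |
| 60% | 0.121 | 0.106 |
| 70% | 0.174 | 0.118 |
| 90% | 0.472 | 0.134 |

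Ten subjects alone give an upward bias of about 0.1. The disease-mix artefact clearly exceeds that only from about 70%. At 90%, 58% of the RA-only tables have an empty margin.

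**Would one RA table over all 22 joints help?** Suppose half the RA subjects are positive at 80% and half at 20% on both scans, with independence within subject. Then m = 0.50, p11 = 0.5(0.64) + 0.5(0.04) = 0.34, p12 = 0.16 and p22 = 0.34. The odds ratio is 0.34²/0.16² = 4.5 and U = 0.096. The same artefact returns through differences between subjects. Resampling subjects would widen the interval but would not remove the bias.

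**The case against.** A reader might infer that the plan commits to pooling the two groups. It does not say so. Pooling is read from the Arm 2 placement, the unrestricted title and the missing group column, and the Data Listing 22 footnote taken alone would make the table RA only. This stands as a limit on certainty. It does not remove the point, because the footnote conflicts with five other places and the population of Table 17 is unstated either way.

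A reader might also take the odds ratios as the size of the problem. Odds ratios are not planned for this endpoint. On the planned coefficient, an odds ratio of 3.2 corresponds to about 0.06 on a 0 to 1 scale, and at 30% to 50% RA positivity splitting does not lower the average sample coefficient at all. This also stands.

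Including controls is legitimate: Protocol 3.1.2.3 describes the HCs as control data and the planar images as a comparison for SPECT/CT. That justifies imaging and reporting them. It does not justify leaving them unidentified in an association table.

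Finally, the endpoint is descriptive, in a 15-subject feasibility arm, with no test or threshold. The risk is misreading, not a wrong decision.

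**Conclusion.** The point holds at low severity. On the natural reading, Tables 17 and 18 combine two groups that differ by construction on the planar margin and probably on the SPECT/CT margin, so some association can appear with none within group. Under the stated assumptions (HC 5% on both scans, equal RA rates on both, within-group independence, 5:10 mix) the spurious symmetric coefficient runs from 0.006 at 30% RA positivity to 0.37 at 90%. It is small up to about 50% and material from about 70%. Which part of that range applies cannot be settled from the documents.

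They therefore do not support saying that the table will produce a false claim of joint-level agreement, only that its layout could not rule one out. Splitting removes the artefact but not the imprecision of 10 subjects per joint. The standard-of-truth label is a separate wording problem and adds nothing to the argument about the mix.

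**What to change.** 1. Add an HC-2/RA group column to Tables 17 and 18 and say so in SAP 4.2.2. Base any predictive-value statement on the RA rows, and show HC-2 as separate counts. If a combined table is kept, add a note that it reflects the HC-versus-RA contrast and the 5:10 mix.
2. Reconcile the Data Listing 22 footnote with Protocol Table 4, Protocol Appendix 1, SAP Table 1, SAP 1.2 and the HC-2 rows of Table 7, so that the SPECT/CT population is stated once.
3. Relabel the SPECT/CT columns of Table 17 as a comparator read.
4. Do not add an unstratified RA table over the 22 joints. Any across-joint summary should be stratified by joint and subject.

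The cost is SAP wording and shell edits; no new data are needed. The downside is that each RA per-joint table holds only 10 subjects, where the coefficient is biased upward by about 0.1 and margins may be empty. The results should be reported as descriptive, with that limitation noted.
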